At the same time, there are scarce data on several aspects of the use of triple FDCs. In particular, the advantages of triple FDCs in comparison with traditional approach to the treatment require complex investigation with the use of outpatient methods of BP measurement of. The effect of triple FDCs on the quality of life (QOL) of hypertensive patients is also of interest.

AIM AND OBJECTIVES OF THE PROGRAM:

To assess the antihypertensive effectiveness effect on the 24-hour BP profile, as well as tolerability of and compliance to the treatment with a triple FDC of amlodipine / indapamide / perindopril arginine in hypertensive patients in the real clinical practice.

Primary endpoints:

• The effectiveness of triple FDC of amlodipine / indapamide / perindopril arginine in terms of BP control in hypertensive patients from the real clinical practice.

Secondary endpoints:

- The 24-hour BP profile on the top of FDC of amlodipine / indapamide / perindopril arginine in hypertensive patients from the real clinical practice.
- Tolerability of the triple FDC of amlodipine / indapamide / perindopril arginine in hypertensive patients from the real clinical practice.
- Compliance with the treatment with triple FDC of amlodipine / indapamide / perindopril arginine in hypertensive patients from the real clinical practice.

DESIGN AND METHODOLOGY

Type of program: Multicenter, observational, non-controlled, open-label program. **Investigators:** Cardiologists and outpatient (primary care) physicians (general practitioners). **Number of patients:** 1,300 hypertensive patients.

The patient is included in the program if prior to the study his/her doctor decided to adjust treatment, targeted at the BP control improvement, by prescription of a triple FDC of amlodipine / indapamide / perindopril arginine. The prescription of the triple FDC of amlodipine / indapamide / perindopril arginine during the program is made by the doctor's decision according to the instructions for medical use of this FDC.

Presumably, each doctor will include 4 patients in average. It is planned to include 1,300 patients.

Time frame of the program

First subject in (FSI):	November, 2018
Last subject last visit (LSLV):	January, 2019
Database lock:	February, 2019
Statistic report:	May, 2019
Clinical study report:	January, 2020.

Inclusion criteria

- Age 18 to 79 years
- Essential hypertension
- Patient's consent to participate in the program

• Doctor's decision to prescribe FDC of amlodipine / indapamide / perindopril arginine, according to the instruction for use, prior to the inclusion in the program.

Non-inclusion criteria

- Symptomatic, or secondary arterial hypertension
- Office BP ≥ 180/110 mm Hg on treatment (at V0 visit)
- History of myocardial infarction, unstable angina, or cerebrovascular accident within the past 1 year
- CHF of class III-IV NYHA
- Type I diabetes or decompensated type 2 diabetes
- Diseases with severe organ dysfunction (hepatic failure, renal failure, etc.)
- Contraindications to or known intolerance of dihydropyridine calcium channel blockers (including amlodipine) and/or indapamide and/or ACE inhibitors (including perindopril) and/or their fixed combination
- Inability to understand the nature of the program and/or to follow the doctor's recommendations, including ones for the BP self-monitoring.

During the program it is planned to perform:

- Office BP measurements. Arterial pressure should be measured in accordance with the recommendations of the European Society for Hypertension (ESH) using an auscultatory or oscillometric method and a semiautomatic sphygmomanometer. Before measurements, the patient should be in the sitting position for 3-5 minutes. The BP is measured on each arm, and the arm with the highest BP value is considered as reference one. Three measurements are carried out on the reference arm when patient is in the sitting position, and the average value of the second and third BP measurements with an interval of at least 1-2 minutes is recorded.
- Pulse rate (HR) measurement.
- Ambulatory blood pressure monitoring (ABPM) (in those patients, in whom it is required, according to the decision of treating physician, based on his/her experience and established practice). The BP will be measured on the non-dominant arm. The measurements will be carried out every 15 minutes in the daytime from 7:00 to 23:00 and every 30 minutes in the nighttime from 23:00 to 7:00.
- *BP self-monitoring*. Throughout the program, with the exception of the days scheduled for ABPM, patients will be keeping diaries of BP self-monitoring. The BP will be measured in a sitting position on the same arm of the working arm after a 5-minute rest with 1-2 minute interval between measurements. It is planned to carry out 3 measurements of BP in the morning after awakening (before breakfast and before taking the study drug) and in the evening before bedtime. In the diary, the average values of the SBP and DBP will be recorded, the BP will be monitored 6 days prior to the visit to doctor.
- Surveys:
 - Assessment of the *patient's quality of life (QoL)* will be carried out using the standardized QoL survey SF36 (Appendix 2).
 - Assessment of the *patient's compliance with the treatment* will be carried out using the compliance questionnaire (Appendix 3).
- Assessment of the treatment tolerability by completion of the standard pharmacovigilance form.

COURSE OF THE PROGRAM

The program will include hypertensive patients, to whom the doctor prescribed the triple FDC of amlodipine / indapamide / perindopril arginine in the routine clinical practice, based on his/her own experience and in accordance with the instruction for medical use of the drug.

Ambulatory Blood Pressure Monitoring [11]: The 24-hour BP profiles: *Dipper*: nighttime BP reduction >10% from daytime values, or ratio "nighttime/daytime BP» is <0.9 and >0.8 [normal 24-hour BP profile].

Reduced dipper: nighttime BP reduction by 1 to 10% from daytime values, or ratio "nighttime/daytime BP» is <1 and >0.9 [reduced 24-hour BP profile].

Non-dipper: Absence of nighttime BP reduction or its increase, or ratio "nighttime/daytime BP» is ≥ 1 [this profile is associated with a high cardiovascular risk].

Extreme dipper: The substantial nighttime BP reduction by >20% from daytime values or ratio "nighttime/daytime BP» is <0.8 [questionable cardiovascular risk].

Nocturnal hypertension: increase in the absolute values of nighttime BP.

Target BP level

In accordance with the guidelines of the Russian Hypertension Society (RMOAG)/Russian Society of Cardiology (VNOK) for the treatment of hypertension (2010, version 4), BP control is defined as office BP <140/90 mm Hg.

Duration of the program: 12 weeks.

During this time, the patient's visits to the doctor are scheduled in accordance with the presented flow chart.

•••				
Time	Week 0	Week 2	Week 4	Week 12
	(V1)	(V2)	(V3)	(V4)
Defining the inclusion/non-inclusion	Х			
criteria	^			
Patient's informed consent	Х			
Medical history, risk factors and lifestyle	Х			
Recording of the current therapy	Х	Х	Х	Х
BP and HR measurements	Х	Х	Х	Х
Body weight and height	Х			
ABPM (in a part of patients)	Х			Х
Issuing the diaries for BP self-monitoring				
Recoding of the data of BP self-		Х	Х	Х
monitoring		^	^	^
Assessment of adverse events		Х	Х	Х
Completion of the QoL questionnaire	Х			Х
Completion of the Treatment compliance questionnaire	Х			X

Flow chart of the program

Visit 1 (inclusion in the program)

- Selection of patients; defining the inclusion/non-inclusion criteria.
- Providing a patient with the Diary for BP self-monitoring and instruction on its completion.
- Carrying out the following examinations:
 - o BP and HR measurements;
 - \circ $\;$ ABPM (in those patients, to whom it was prescribed by the doctor).
- Recoding of the current therapy; completion of the questionnaires:
 - SF36 questionnaire for the QoL assessment (Appendix 2);
 - Patient's treatment compliance questionnaire (Appendix 3).

Visit 2

- Carrying out the following examinations:
 - o BP and HR measurements;
 - Control of the completion of BP self-monitoring diary by a patient.
- Antihypertensive treatment at the time of visit.
- Assessment of the adverse events.

Visit 3

- Carrying out the following examinations:
 - o BP and HR measurements;
 - o Control of the completion of BP self-monitoring diary by a patient.
- Antihypertensive treatment at the time of visit.
- Assessment of the adverse events.

Visit 4. Completion of the program

- Carrying out the following examinations:
 - o BP and HR measurements;
 - \circ ABPM (in those patients, to whom it was prescribed by the doctor).
- Antihypertensive treatment at the time of visit.
- Completion of the questionnaires:
 - SF36 questionnaire for the QoL assessment (Appendix 2);
 - Patient's treatment compliance questionnaire (Appendix 3).
- Assessment of the adverse events.

• Collection of the diaries of BP self-monitoring.

CONCOMITANT TREATMENT

The treatment with any drugs, including antiplatelets, statins, nitrates, anti-inflammatory or other drugs, is determined by the treating physician.

Diet and physical activity

During the program there will be no additional restrictions of diet or physical activity.

Collecting and reporting the safety data

1. Definitions

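### The plan does not require consecutive inclusion of eligible FDC patients or record those left out, so the control rate is open to selection that its confidence interval does not cover

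*Combined protocol and SAP*

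**What the plan says.** The aim is to assess effectiveness, tolerability and compliance "in hypertensive patients in the real clinical practice". The design is a "Multicenter, observational, non-controlled, open-label program". BP control, the basis of the primary endpoint, is office BP below 140/90 mm Hg (Target BP level), and the Statistical analysis section plans 95% confidence intervals for the percentages.

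On who enters, the plan gives four things:

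- **Condition for entry** (Design and Methodology): "The patient is included in the program if prior to the study his/her doctor decided to adjust treatment" by prescribing the FDC. The inclusion criteria repeat that the prescribing decision is made "according to the instruction for use, prior to the inclusion in the program".
- **A criterion that needs judgement** (Non-inclusion criteria): "Inability to understand the nature of the program and/or to follow the doctor's recommendations".
- **A step at Visit 1**: "Selection of patients; defining the inclusion/non-inclusion criteria", with no method of selection.
- **Numbers** (Design and Methodology): "Presumably, each doctor will include 4 patients in average", followed by "It is planned to include 1,300 patients".

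The average of 4 is an expectation, not a quota. The reviewed text has no rule for consecutive, all-comer or random inclusion. It has no log of eligible patients who were not included, and the analysis section has no check of representativeness.

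**The concern.** The criteria settle who may be included. They do not settle which of a doctor's eligible FDC patients are included. Treatment is open-label and the doctor knows the patient, so inclusion can depend on how the doctor expects that patient to attend, comply or respond. Compliance and tolerability are endpoints too and are exposed in the same way.

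In a controlled trial, selection at entry acts on all arms. Here there is one group and the absolute rate is the result, so nothing cancels. A larger sample does not help: it narrows the interval around whatever value the selection produces. Because eligible patients left out are not recorded, nobody could later show that selection was absent or small.

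**Working it through.** The plan gives no expected control rate, precision target or sample-size calculation, so it has no figure of its own to reproduce. Only 1,300 patients, the average of 4 per doctor, the 95% level and the dates come from the documents. All other inputs are assumptions.

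**1. What the interval covers.** Half-width = 1.96 × √(p(1−p)/n). At an assumed p = 0.75 and n = 1,300: 1.96 × √(0.75 × 0.25/1300) = 1.96 × 0.01201 = 0.0235, or about 2.4 points. At other rates it is 2.7 (p = 0.5), 2.5 (0.7), 2.2 (0.8) and 1.6 (0.9). This assumes all 1,300 contribute and ignores clustering by doctor.

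**2. An illustrative selection model.** Let a share s of eligible patients be less promising (control 50%) and the rest more promising (85%). Let the less promising be included r times as often.

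- True rate = 0.85 − 0.35s
- Less promising share among those included: s′ = sr/(sr + 1 − s)
- Bias = (s − s′) × 35 points

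| s | r | s′ | True rate | Rate in included | Bias (points) |
|---|---|---|---|---|---|
| 0.2 | 0.75 | 0.158 | 78.0% | 79.5% | 1.5 |
| 0.3 | 0.75 | 0.243 | 74.5% | 76.5% | 2.0 |
| 0.4 | 0.75 | 0.333 | 71.0% | 73.3% | 2.3 |
| 0.2 | 0.5 | 0.111 | 78.0% | 81.1% | 3.1 |
| 0.3 | 0.5 | 0.176 | 74.5% | 78.8% | 4.3 |
| 0.4 | 0.5 | 0.250 | 71.0% | 76.25% | 5.25 |

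All three r = 0.75 rows lie inside 2.35 points, the last only just. All three r = 0.5 rows lie outside.

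**3. Dependence on the 35-point gap.** Bias is (s − s′) times the gap. At the most selective corner (s = 0.4, r = 0.5) the factor is 0.15. A 10-point gap then gives 1.5 points, and the gap must exceed 2.35/0.15 = 15.7 points to pass the half-width. At s = 0.2, r = 0.5 it must exceed 2.35/0.0889 = 26.4 points.

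**4. Dependence on the share included.** Put differently, let f be the share of eligible patients included and d the difference in control rate between those included and those left out. Bias = (1 − f) × d, which equals the half-width when d = 2.35/(1 − f). That is 4.7 points at f = 0.5, 9.4 at f = 0.75 and 23.5 at f = 0.9.

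**5. How large f might be.** First subject in is November 2018, last subject last visit is January 2019, and follow-up is 12 weeks. From 1 November to 31 January is 91 days; less 84 days, about 7 days remain for enrolment. Few new FDC prescriptions per doctor may fall in that window, so f could be high. The documents do not say.

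**The case against.** The strongest reply is that the plan nowhere invites doctors to pick. The entry sentence can be read as taking every patient for whom the FDC was chosen, and the Visit 1 step sits beside the eligibility check. With no quota, no shortage of places forces a choice. The enrolment window is short, so 4 patients may be most of what a doctor has. This has weight: it makes a high f plausible, and at f = 0.9 the bias stays inside the interval unless d exceeds about 23 points. It does not close the gap. The sentence states a condition for entry, nothing tells the doctor to offer the program to all, and without a record f stays unknown.

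A reader might infer that the control rate is overstated by more than its confidence interval. The documents do not support that. Half of the illustrated cases fall inside the half-width, and the rest need a foreseeable gap well above 10 points. Nor is the direction fixed. The FDC is prescribed to improve BP control, so doctors might favour their difficult patients, which would lower the rate.

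A reader might also blame the missing limit on patients per doctor. That affects clustering and the weight of heavy recruiters. At p = 0.5 and an assumed intracluster correlation of 0.10, the half-width is 3.1 points with exactly 4 per doctor and 3.5 to 4.0 with very uneven numbers (coefficient of variation 1 to 1.5). It is not a source of selection bias.

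**Conclusion.** The point holds as a gap in design and reporting. The plan sets eligibility without requiring consecutive inclusion, keeps no record of eligible patients left out, and reports an absolute rate for real practice whose interval covers sampling error only.

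The size is not known. Under the assumed 85% and 50% control rates, with 20-40% of eligible patients in the lower group, the bias is 1.5 to 2.3 points at r = 0.75 and 3.1 to 5.25 points at r = 0.5, against a half-width of about 2.4. Smaller gaps, or inclusion of nearly all eligible patients, keep it inside. So selection could matter as much as sampling error, but the documents do not show that it does, or in which direction. The case for acting is that the remedy is cheap and the question cannot be answered afterwards without it.

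**What to change.** In Design and Methodology, require each doctor to offer the program to every consecutive eligible patient already prescribed the FDC, from site start until that doctor's enrolment ends. If the rule is fully followed and every patient offered accepts, f = 1 and this source of bias is zero. Refusals would remain, and the log would show how many.

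Keep an anonymous count log per doctor of patients eligible, offered and included, with the reason for each non-inclusion. Report the included share. Add age group, sex and BP of non-included patients only if the ethics committee allows it, because they have not given the written consent that Ethical considerations requires before participation.

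In Statistical analysis, state that the confidence interval covers sampling error only. A maximum per doctor should not be offered as the remedy for selection. If enrolment is already over, the report should say that selection among eligible patients was not documented.

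The cost is a short amendment and modest paperwork at about 325 doctors (1,300/4, if the expected average holds). No visit, test or treatment decision changes, since prescription already precedes inclusion.

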- Percentage (%) of patients at the target levels of the office BP (SBP <140 mm Hg and DBP <90 mm Hg): in general sample and in subgroups (men, women, patients with IHD, diabetes, metabolic syndrome, ISAH, and patients older than 65 years)
- Change in the proportion of patients with different 24-hour BP profiles (dipper, non-dipper, reduced dipper, extreme dipper, nocturnal hypertension)
- Mean change in the 24-hour SBP and DBP (in mm Hg) in patients who performed ABPM
- Mean change in the daytime SBP and DBP (in mm Hg) in patients who performed ABPM
- Mean change in the nighttime SBP and DBP (in mm Hg) in patients who performed ABPM
- Percentage (%) of patients at the target levels of the office BP (24-hour SBP <135 mm Hg and DBP < 85 mm Hg) in patients who performed ABPM
- Change in the mean score of the SF-36 survey (Appendix 2)
- Changes in the treatment compliance score by the Compliance questionnaire (Appendix 3)
- List of SAEs
- List of AEs
- List of AEs that resulted in the withdrawal of the triple FDC of amlodipine / indapamide / perindopril arginine.
- List of ADR
- List of SADR
- List of special situations

Statistical parameters

All parameters will be analyzed using the methods of descriptive statistics. For each parameter, the number of patients, mean, standard error, minimum and maximum values will be indicated.

Statistical analysis

- The baseline characteristics will be analyzed in all the patients who started the treatment (intention-to-treat [ITT] population). In case of significant differences between two treatment groups, the baseline characteristics will be provided for both of them.
- Changes in the SBP and DBP (with the corresponding confidence intervals) will be assessed in the patients who completed the program without major deviations from protocol (per-protocol population [PPP]).
- The analysis of parameters with normal distribution will be performed using the Student's t-test for paired measurements; otherwise the non-parametric Wilcoxon test will be used. The percentage of patients with normalized BP, as well as the percentage of patients who responded to treatment (with 95% confidence intervals), will be calculated.
- Questionnaires: The score for each scale will be calculated as the sum of scores for questions constituting the scale.
- Assessment of the AEs will be carried out in all the patients who started the treatment (ITT population).

Administrative aspects

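### Do the November 2018 to January 2019 milestones leave room for 12 weeks of follow-up in 1,300 patients?

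*Combined protocol and SAP*

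**What the plan says.** The protocol states "Duration of the program: 12 weeks". The sentence after it places each patient's visits within that period, and the flow chart runs from week 0 (V1) through weeks 2 and 4 to week 12 (V4). V1 is the inclusion visit; the last visit is headed "Visit 4. Completion of the program". No window around V4 is given.

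The section Time frame of the program lists months without days: first subject in "November, 2018", last subject last visit in January 2019, database lock in "February, 2019", and the statistical report in May 2019. On size, Design and methodology says "Presumably, each doctor will include 4 patients in average. It is planned to include 1,300 patients". Under Inclusion criteria, the decision to prescribe the fixed-dose combination must come "prior to the inclusion in the program".

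Under Statistical analysis, changes in systolic and diastolic pressure "will be assessed in the patients who completed the program without major deviations from protocol". No analysis there refers to a calendar date.

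**The concern.** Enrolment and follow-up have to fit one after the other between first subject in and last subject last visit. Twelve weeks of follow-up take up nearly all of the time between November and January, so almost nothing seems to be left for recruiting 1,300 patients. The obvious suspicion is that one of the three dates is an entry error.

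V4 is the only visit after baseline with ambulatory monitoring, SF-36 and the compliance questionnaire. These feed the 24-hour profile and compliance secondary endpoints and the quality-of-life analysis. If sites held to January while enrolment ran on, late enrolees could miss V4 or have it early, and some could drop out of the per-protocol analysis of blood pressure change.

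**Working it through.** **Inputs.** First subject in no earlier than 1 November 2018 and last visit no later than 31 January 2019 (Time frame of the program, taking the most favourable day of each month). Follow-up 12 weeks = 84 days (Duration of the program and flow chart). 1,300 patients at about 4 per doctor (Design and methodology). The protocol gives no enrolment figure to reproduce.

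**Slack.** 1 November to 31 January = 91 days; 91 - 84 = 7 days.

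**Inclusion dates, with V1 as day 0 and V4 no earlier than day 84.** 31 January minus 84 days = 8 November. Inclusion can fall on 1-8 November: 8 dates, 6 of them weekdays. The earliest possible last visit is 1 November + 84 days = 24 January. A patient included on 9 November reaches day 84 on 1 February.

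**Load.** Doctors: 1,300 / 4 = 325. Patients per weekday: 1,300 / 6 = 217. Per doctor per weekday: 4 / 6 = 0.67.

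**Sensitivity to the convention for week 12.** The plan says only week 12, so these are assumptions:

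| Earliest V4, days after V1 | Last inclusion date | Dates | Weekdays | Patients per weekday |
|---|---|---|---|---|
| 84 | 8 November | 8 | 6 | 217 |
| 83 (same as counting V1 as day 1) | 9 November | 9 | 7 | 186 |
| 77 (7 days early) | 15 November | 15 | 11 | 118 |
| 70 (14 days early) | 22 November | 22 | 16 | 81 |

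With the 7-day allowance the load is 4 / 11 = 0.36 per doctor per weekday.

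**If enrolment ran to 30 November (assumed).** The last V4 would be 30 November + 84 days = 22 February 2019, six days before the end of the stated lock month. If January were enforced instead, a patient included on 30 November would have at most 62 days (8.9 weeks) by 31 January.

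**Can the 12 weeks mean the whole program?** No. The flow chart counts weeks from each patient's own inclusion. If the whole program lasted 12 weeks, all patients would have to enter on one day.

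**The case for a change.** The strongest case for a change is that the fit is very narrow. Of the 30 x 31 = 930 pairs of a November start day and a January end day, only 8 + 7 + ... + 1 = 36 let even one patient complete 84 days. (This is a count, not a probability.) About 325 doctors would have to start almost together, and the available text gives no enrolment period or site-start plan. With no V4 window, nothing says whether a visit at 62 days counts as week 12 or as a major deviation. Correcting the dates would cost almost nothing.

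The arithmetic stands, and so does the absence of a stated window from the available text. The step from there to a defect does not.

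- A tight schedule is not a contradiction. The program is observational, the prescribing decision precedes inclusion, and four patients per doctor is a small quota. Whether the doctors could start together is an operational judgement on which the available text is silent, and part of the front matter is missing from that text.
- The 36-of-930 count depends on V1 being day 0 and V4 falling no earlier than day 84, which the plan does not say.
- The harm needs the January date to be enforced against individual patients, and nothing in the plan requires this. Even then, a patient seen early would still supply the final ambulatory, SF-36 and compliance data. Exclusion from the per-protocol set would depend on what counts as a major deviation, which is not defined.

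**Conclusion.** The concern does not call for a change. At the most favourable days of each month the schedule leaves 7 days of slack, which means inclusion on 1-8 November if V4 is never before day 84, or up to 15 November with an assumed 7-day allowance. That is ambitious but possible, and the documents do not show any date to be wrong.

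The milestones read as forecasts rather than data cut-offs. If enrolment took longer, the last visit would move into February or beyond and lock might follow, with some room before the May 2019 report; every patient would still be followed to week 12. No estimate, analysis population or conclusion depends on the calendar months. The number of patients affected if the dates were enforced cannot be derived from the documents.

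This rests on two assumptions: that the team lets the dates slip rather than cutting follow-up short, and that the handling of early or late V4 visits is settled when major deviations are classified before lock. Both are ordinary practice. Confirming the dates and noting the enrolment period and V4 window would be a courtesy to the reader and would change no result.

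### The control rate counts every patient below 140/90 whatever they are taking, so it cannot show how many were controlled on the triple FDC without added antihypertensives

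*Combined protocol and SAP*

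**What the plan says.** The document is a combined protocol and SAP for a single-group, 12-week observational program in a planned 1,300 patients.

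- **Primary endpoints:** "The effectiveness of triple FDC of amlodipine / indapamide / perindopril arginine in terms of BP control", in hypertensive patients seen in routine practice.
- **Target BP level:** "BP control is defined as office BP <140/90 mm Hg".
- **Effectiveness and tolerability variables:** "Percentage (%) of patients at the target levels of the office BP (SBP <140 mm Hg and DBP <90 mm Hg): in general sample", and in named subgroups. None of the subgroups is defined by treatment.
- **Concomitant treatment:** "The treatment with any drugs, including antiplatelets, statins, nitrates, anti-inflammatory or other drugs, is determined by the treating physician".
- **Flow chart:** "Recording of the current therapy" is marked at weeks 0, 2, 4 and 12. The descriptions of Visits 2, 3 and 4 each list "Antihypertensive treatment at the time of visit".
- **Statistical analysis, control rate:** "The percentage of patients with normalized BP, as well as the percentage of patients who responded to treatment" will be calculated with 95% confidence intervals. No analysis population is named for these percentages.
- **Statistical analysis, mean change:** changes in SBP and DBP "will be assessed in the patients who completed the program without major deviations from protocol (per-protocol population [PPP"). Major deviations are not defined.

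Two planned outputs touch on treatment failure: a list of adverse events that led to FDC withdrawal, and a list of special situations, which by the safety definitions include lack of efficacy. Neither is linked to the control rate.

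**The concern.** The endpoint names one product, while the variable that measures it makes no reference to treatment. Office BP is measured at weeks 2 and 4, so a physician who sees a patient above target has at least eight weeks to act before the final reading. Three kinds of patient would then count as controlled in a rate presented as the FDC's effectiveness: one who received a further antihypertensive, one who was switched to another regimen, and one who stopped the FDC but still attended Visit 4.

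The program has no comparator, so the control rate is its main evidence on effectiveness. If the reader cannot separate control on the FDC as started from control after a change, the report cannot say which of the two it shows. The therapy records needed to separate them are taken at every visit, but no planned analysis uses them.

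**Working it through.** **1. Does any text condition the control rate on treatment?**

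| Place | Condition on treatment? |
|---|---|
| Target BP level (definition of control) | None; a BP threshold only |
| Effectiveness variables (control rate) | None; whole sample and clinical or demographic subgroups |
| Statistical analysis (percentage normalized) | None; no population named |
| Statistical analysis (SBP/DBP change) | Per-protocol set, for mean change only; major deviations undefined |
| Concomitant treatment | Physician decides; no antihypertensive restricted |
| Withdrawal and special-situation lists | Listings only |

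The per-protocol set does not settle the question. It is not stated for the control rate. Where it is stated, a drug added under the concomitant-treatment clause is not evidently a deviation, and whether stopping the FDC would be one is not said.

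**2. Form of the gap.** Let *f* be the share of patients who added, substituted or stopped treatment by Visit 4, *c* the control rate among them, and *r* the control rate among the rest. With a common denominator:

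- rate regardless of treatment = (1 − f)·r + f·c
- rate on the FDC with nothing added = (1 − f)·r
- gap = f·c, which cannot be negative

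**3. Scale.** There is no plan figure to reproduce: 1,300 is given without an expected rate, a precision target or a rate of treatment change. The values of *f*, *c* and *r* below are assumptions, with r = 80%.

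| f | c | Regardless of treatment | On FDC, nothing added | Gap (points) |
|---|---|---|---|---|
| 2% | 40% | 79.2% | 78.4% | 0.8 |
| 5% | 60% | 79.0% | 76.0% | 3.0 |
| 10% | 60% | 78.0% | 72.0% | 6.0 |
| 20% | 80% | 80.0% | 64.0% | 16.0 |

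Worked line: 0.95 × 0.80 + 0.05 × 0.60 = 0.76 + 0.03 = 0.79, and the gap is 0.05 × 0.60 = 0.03.

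**4. Comparison with sampling error.** The 95% half-width is 1.96 × √(p(1 − p)/1,300).

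- p = 80%: 1.96 × √(0.16/1,300) = 2.17 points
- p = 50%: 1.96 × √(0.25/1,300) = 2.72 points

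This treats all 1,300 patients as independent and evaluable. On these assumptions a gap of 3.0 points exceeds the half-width at either rate, and a gap of 0.8 points exceeds neither.

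**The case against.** The strongest reply is that the endpoint concerns routine practice. The program is observational and prescribing is the doctor's decision, so control at 12 weeks after starting the FDC, whatever followed, is a legitimate quantity to estimate. That stands. A reader might infer that the overall rate is wrong and must give way to one in which any treatment change counts as failure. The documents do not require this, and choosing between the two as primary is a trade-off.

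Second, the drugs named in the concomitant-treatment clause are not chiefly antihypertensives. A reader might take the clause as express permission for add-ons, but it is not that. The point rests on its general wording, on the absence of any restriction elsewhere, and on the repeated recording of antihypertensive treatment. This narrows the point without removing it.

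Third, some failures and withdrawals would appear in the safety listings. That is true, but listings do not alter or qualify the control rate.

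Fourth, some patients who changed treatment may already have been controlled, for example those who left the FDC for tolerability. The documents do not show that changes go only to patients who are failing. The gap f·c is therefore control not shown on the FDC as started. It is not a proven excess.

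Finally, the visit records may not map cleanly. Therapy at Visit 1 could mean the regimen before the FDC, and treatment at Visit 4 could include drugs prescribed after the final reading. This is a fair caution, and the derivation rule has to deal with it.

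**Conclusion.** The point holds as a gap in how the primary result is specified and reported. The control rate takes no account of treatment, the therapy records are unused, and no rule says how added, substituted or stopped antihypertensives count. Relative to control on the FDC with nothing added, the overall rate can only be equal or higher when both use the same denominator.

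The size is unknown. The 3.0-point example rests entirely on assumed values (5% changed, 60% of them controlled), and the assumed range runs from 0.8 to 16.0 points. A reader might take any of these figures as the expected bias, but the documents give no rate of treatment change to support that.

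A reader might also conclude that a rate limited to unchanged patients would isolate the effect of the FDC. It would not. There is no comparator, and patients may already have been taking other antihypertensives when the FDC was started.

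**What to change.** In the statistical analysis section:

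1. Keep the overall Visit 4 control rate and label it as control regardless of treatment changes.
2. Pre-specify a second rate beside it. The denominator is all patients who started the FDC. The numerator is those below 140/90 at Visit 4 who are still on the FDC with no antihypertensive added after it was started.
3. Classify patients by treatment taken up to the Visit 4 reading, not by drugs prescribed at that visit. Define baseline therapy so that the regimen before the FDC is not read as a later change.
4. State how starters without a Visit 4 BP count, and name the denominator of the overall rate. If the two denominators differ, the gap also includes loss to follow-up.
5. Tabulate added, substituted and stopped antihypertensives by visit.

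Do not compare mean SBP or DBP change across the treatment groups so formed. Membership is decided after baseline, and if add-ons go to poor responders, the unchanged group is enriched for good ones. Do not describe the second rate as a causal effect of the FDC.

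The cost is some SAP wording, one extra table from the visit records, and a second rate likely to be somewhat lower than the overall one. Clinical management does not change.
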